4.3 Handling of repeated and unscheduled measurements

All repeated and unscheduled measurements will be presented in the listings, where applicable. The following general rules will apply to all repeated and unscheduled measurements:

- For repeated and unscheduled measurements obtained prior to the first dose of UCB7665 the latest value (which may be scheduled or unscheduled) will be used in the calculation of descriptive statistics;
- For repeated and unscheduled measurements obtained at the designated Baseline visit, the latest value (which may be scheduled or unscheduled) will be defined as the Baseline provided that this occurred prior to the first dose of UCB7665;
- For repeated measurements obtained at any timepoint after the first dose of UCB7665, the first value of any repeated measurements will be used in the calculation of changes from Baseline and for the descriptive statistics. Unscheduled and repeated measurements will not be included in the descriptive statistics at timepoints after the first dose of UCB7665, however they may be included in any summaries for abnormal measurements.

The above rules are not applicable for the determination of the response variables for the platelet measurements; both scheduled and unscheduled measurements may be used in the calculation of response, time to response and duration of response ([Section 8.1.1](#)).

4.4 Interim analyses and data monitoring

For the sequential adaptive design in this study, at least 11 interim analyses will be performed. Safety data from the interim analyses will be reviewed by the DMC to monitor the safety, to adapt the dose regimen, and to decide when and if the UCB7665 7mg/kg weekly group (Dose Arm 2), UCB7665 10mg/kg weekly group (Dose Arm 3), UCB7665 15mg/kg group (Dose Arm

4) and UCB7665 20mg/kg group (Dose Arm 5) should be opened, as well as whether the doses in any of the treatment groups should be modified.

A detailed description of the DMC composition, processes and responsibilities will be provided in a separate DMC Charter. The data required for review as well as the timing of each interim analysis is described in a separate interim SAP and includes all data specified in the DMC Charter, which is available at the time. For the interim analyses the data, subject to analysis, should be as clean as possible; however, the database will not be locked and a snapshot will be taken.

4.5 Multicenter studies

Individual center results will not be displayed.

4.6 Multiple comparisons/multiplicity

Not applicable.

4.7 Active-control studies intended to show equivalence

Not applicable.

4.8 Examination of subgroups

The following subgroups will be defined within each dose arm:

- Concomitant corticosteroid medication: Yes/No

Concomitant medication is defined in Section 6.4.4. The list of applicable Anatomical Therapeutic Chemical (ATC) codes to be utilized as corticosteroids is provided in Section 13.1.

- Responder at the end of past ITP therapy: No/Yes/Unknown

Responder categories will be defined utilizing the value (either Yes or No) for the last reported ITP therapy for each patient. If this value is unknown, the second-last reported ITP therapy value will be used, then the third-last, and so on, until a known response is provided. The Unknown responder category will only be considered in cases where the investigator has never reported a category (Yes or No) for any of the past ITP therapies. For the 'Response' definition, the CRF entries will be utilized.

The past ITP therapy is defined as procedure history related to ITP or past medication related to ITP, where past medication is defined in Section 6.4.1. For 'related to ITP' CRF entries will be utilized.

The corticosteroid medication given more than 3 months prior to screening was routinely not recorded and cannot be considered. Thus, some patients with an unknown response might have had a known response.

- Past intravenous immunoglobulin (IVIg) medication: Yes/No

Past medication is defined in Section 6.4.1. The ATC Therapeutic Subgroup code (Level 2) 'IMMUNE SERA AND IMMUNOGLOBULINS' will be utilized.

- Number of past ITP therapies: $\leq 2 / > 2$

The past ITP therapy is defined as procedure history related to ITP or past medication related to ITP, where past medication is defined in Section 6.4.1. For ‘related to ITP’ CRF entries will be utilized.

The corticosteroid medication given more than 3 months prior to screening was routinely not recorded and cannot be considered. Thus, some patients might have had 1 more past ITP therapy than utilized for subgroup determination.

The descriptive summaries for platelets and total IgG will be presented for the subgroups above.

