3.5.4 Per Protocol Set

The Per Protocol Set (PPS) is a subset of the FAS, consisting of those subjects who had received all foreseen sc infusions, had a platelet count measurement (measured by ACM Global Central Laboratory) during the Observation Period, and no important protocol deviations that may potentially affect the platelet count as confirmed during a pre-analysis review of the data prior to database lock. Protocol deviations may not necessarily lead to total exclusion of a subject from the PPS but may lead to exclusion of specific data and/or timepoints from the analysis.

Platelet data for subjects who have taken prohibited medications potentially affecting platelet counts such as IV corticosteroids, TPO-Rs, Oral corticosteroids, immunosuppressants (based on medical review) will only be utilised in the summary tables, up to the start date of these prohibited medications.

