6.4.3 Baseline medication definition

Baseline medications will include any medications that started prior to dosing and continued after (classified as prior and concomitant medications).

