6.4.4 Concomitant medication definition

Concomitant medications will include any medication that has been taken at least once (after the first administration of UCB7665) during the Dosing Period and/or the Observation Period.

This includes medications that started prior to the dosing and continued after (classified as prior and concomitant medications) as well as any medication that started after the first administration of UCB7665 (classified as concomitant).

Any medications with missing dates and/or times will be handled as described in [Section 4.2.7](#) in order to classify them as prior and/or concomitant.

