8.1.4 Rescue medication definition (after medical inspection)

In the rescue medication section of the protocol, rescue medication is defined as platelet substitution or treatment with a commercially available IVIg. In addition, the prohibited medications PLEX, dexamethasone and rituximab will also be considered as a rescue medication for analysis.

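### The corticosteroid subgroup counts corticosteroids first started after dosing, so membership can depend on the platelet result being summarised; the SAP's own Baseline medication class avoids this

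*SAP*

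**What the plan says.** Section 4.8 lists four subgroups within each dose arm. Three rest on past therapy or procedure history and are fixed before dosing. The fourth is "Concomitant corticosteroid medication: Yes/No", with concomitant defined in Section 6.4.4 and the drug codes in Section 13.1.

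Section 6.4.4 covers "any medication that has been taken at least once (after the first administration of UCB7665) during the Dosing Period and/or the Observation Period". It includes drugs carried over from before dosing "as well as any medication that started after the first administration of UCB7665 (classified as concomitant").

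Section 6.4.3 defines a narrower class: "Baseline medications will include any medications that started prior to dosing and continued after". Section 4.8 does not use it.

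Platelet summaries (8.1.2) and responder rates (8.1.3.3) are repeated by subgroup on the FAS only. Total IgG (9.2.2) is repeated by subgroup on the PD-PPS.

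The rules on added drugs also matter here. FAS platelet data are cut at the start of rescue medication (3.5.3, 8.1), and Section 8.1.4 says "the prohibited medications PLEX, dexamethasone and rituximab will also be considered as a rescue medication for analysis". Section 3.5.4 names intravenous and oral corticosteroids among prohibited drugs that may affect platelets, but that cut applies to the PPS.

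**The concern.** Grouping on something that happens after treatment starts is safe only if it is unrelated to the outcome. Here the SAP itself supplies the link: it analyses one corticosteroid as rescue and treats others as able to change counts. A subject whose platelets stay low and who starts a corticosteroid in the last weeks of the 8-week Observation Period moves from No to Yes for all visits, including those before the start. The Yes group gains a poor early course and the No group loses a non-responder.

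What is at stake is how these tables are read. A gap between users and non-users could be created by the grouping rule alone. With 15 subjects per arm, or 6 to 12 in Dose Arms 3 to 5, one or two moved subjects visibly change a percentage.

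**Working it through.** **The plan's own figure.** The SAP gives no number for this subgroup. The nearest is Section 2.4: power above 80% with 15 subjects for 50% response against 15%. Exact binomial: requiring at least 6 responders of 15 gives one-sided alpha 0.017 and power 0.849, which agrees. Only the 50% is borrowed below.

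**Do existing rules repair the grouping?**
- The FAS cut at dexamethasone removes later counts, but the subject stays in Yes with the earlier low counts and is missing from No.
- Other corticosteroids do not trigger the FAS cut. The wider cut is for the PPS, while the platelet subgroup tables are FAS only.

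**Illustration with no true association between corticosteroids and response.** Inputs:
- p = response rate, 50% (Section 2.4)
- b = share on a corticosteroid at Baseline (assumption, 10% to 50%)
- q = share of non-responding Baseline non-users who start one (assumption, 0% to 50%)
- s = share of those starters whose later counts register as a response (assumption, 0 to 1; 0 where data are cut at the start)

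Formulas:
- share of the arm moved, m = (1 − b)(1 − p)q
- Yes rate = (bp + ms)/(b + m)
- No rate = (1 − b)p/((1 − b) − m)

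At b = 30%, q = 30%, s = 0: m = 0.7 × 0.5 × 0.3 = 0.105; Yes = 0.15/0.405 = 37.0%; No = 0.35/0.595 = 58.8%.

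| q (p = 50%, b = 30%) | No | Yes, s = 0 | Gap, s = 0 | Yes, s = 1 | Gap, s = 1 |
|---|---|---|---|---|---|
| 0% | 50.0% | 50.0% | 0 | 50.0% | 0 |
| 10% | 52.6% | 44.8% | −7.9 | 55.2% | +2.6 |
| 30% | 58.8% | 37.0% | −21.8 | 63.0% | +4.1 |
| 50% | 66.7% | 31.6% | −35.1 | 68.4% | +1.8 |

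Gaps are in percentage points, from unrounded rates.

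With s = 0 and q from 10% to 50%, the gap at p = 50% runs from −5.0 (b = 50%, q = 10%) to −51.3 (b = 10%, q = 50%). At p = 30% it runs from −4.2 to −38.9. With s = 1 the sign can reverse: +19.9 at p = 50%, b = 10%, q = 30%.

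**Grouping by Baseline use instead.** Nobody moves, so Yes = p and No = p + (1 − p)qs. With s = 0 both are 50% for any b and q. With s = 1 and q = 30%, No = 0.5 + 0.5 × 0.3 = 65% against 50%, a gap of −15 points. That remainder comes from counts after the added drug, not from the grouping. In this corner it exceeds the +4.1 above, so post-dose starters need to be visible.

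**The case against.** The case against is strong on size and reach:

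- **Few or no starters.** The SAP calls corticosteroids prohibited medication in Section 3.5.4, so post-dose starts may be rare. This stands: with none the bias is zero, and the documents give no count.
- **Cause is not shown.** The Section 13.1 code list is not in the text at hand, so topical or inhaled products, or use for another condition, may count. A late starter may also be an early responder who lost response. This stands; the documents support only that membership *can* depend on the outcome.
- **Descriptive only.** No subgroup test is planned and the primary objective is safety. This stands; only interpretation is affected.

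A reader might go further and infer any of the following. The documents do not support them:

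- *The No group is cleared of failures.* Failures managed with IVIg, platelets, PLEX or rituximab, without a corticosteroid, remain in No.
- *The Yes group carries all later steroid-driven counts.* Counts after dexamethasone are already cut; only those after other corticosteroids remain.
- *The IgG comparison is biased in the same way.* The effect needs a further link between platelet failure and IgG reduction. Those tables use the PD-PPS and are also cut at rescue.
- *Subjects with other immunoglobulins are counted as past IVIg users.* Section 4.8 applies "The ATC Therapeutic Subgroup code (Level 2") for immune sera and immunoglobulins, broader by name than its intravenous label. What the group contains, and whether any subject is affected, is not in the documents.

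**Conclusion.** The definitional fault is in the text. Section 4.8, through Section 6.4.4, makes corticosteroid subgroup membership a post-dose variable, and the SAP's rescue and prohibited-medication rules tie that variable to platelets. The FAS platelet and responder tables by this subgroup can therefore be biased in either direction.

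The size is not known. It rests on the number of post-dose starters, why they started, and whether their later counts stay in the FAS. The −8 to −35 points above are conditional on assumed values, not an estimate for this trial. To say that every subgroup difference is uninterpretable would go too far. The point merits a correction because the tables could mislead and the SAP already holds a better class.

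**What to change.** 1. In Section 4.8, define the subgroup as Baseline corticosteroid medication, Yes/No, using Section 6.4.3 and the Section 13.1 codes.
2. Add a date rule for this subgroup. Section 4.2.7 sets an unknown start date, and some partial ones, to the day of first dosing, and classes a start on that day as concomitant. A long-standing corticosteroid could then fall out of the Baseline class. State that a corticosteroid still in use after first dosing, with an unknown or partial start date not shown to be after first dosing, counts as Baseline here.
3. Keep the existing FAS rescue cut, and flag or list subjects who start a corticosteroid after dosing.

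The cost is a few lines of SAP wording on data already collected and coded. There are two small downsides. The extra date rule may place an occasional true post-dose starter in Baseline. Counts after corticosteroids other than dexamethasone also stay in the FAS tables, so the flag is needed to read them.

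Secondary and optional: align the past-IVIg rule with its label by using preferred term and route, both available under Section 6.4.

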6.4 Past, prior, baseline and concomitant medications

Past, prior, baseline and concomitant medications will be summarized for the SS by dose arm and for all subjects by WHODD Anatomical Main Group [Level 1], Therapeutic Subgroup [Level 2] and PT.

All medications will be listed and will include coding information, reported term, dose per intake and unit, frequency, formulation, route of administration, indication, category (past/prior and concomitant/concomitant) and start and end date (or ongoing, if applicable).

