6.4.1 Past medication definition

Past medications will include any medications that started and stopped prior to the first administration of UCB7665.

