All response variables described above will be listed by dose arm and subject and summarized by dose arm and visit where appropriate. The responder rates will be tabulated as described in [Section 8.1.3.3](#). Moreover the change in category of bleeding from Baseline will also be presented in shift table at all post-Baseline visits by dose arm. Summary tabulations for Clinical Response by dose arm will be repeated according to past intravenous immunoglobulin medication (Yes/No) and the number of past ITP therapies (≤ 2 / > 2). All analyses described in this section will be performed for the FAS.

In case rescue medications are taken, only the data up to (not including) the start date of rescue medication will be utilized for the summary tables. Listings will contain all the data but a footnote will be included indicating the patients for which some data has been excluded from the summary tables. In case of partial dates, the imputation rules for partial dates described in [Section 4.2.7](#) will be applied.

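### The past-IVIg subgroup in SAP section 4.8 is assigned from a drug class wider than IVIg, so the rule does not match its label

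*SAP*

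**What the plan says.** Section 4.8 lists four subgroups to be formed within each dose arm. One is "Past intravenous immunoglobulin (IVIg) medication: Yes/No". Its assignment has two parts. The first is the general definition in section 6.4.1: "Past medications will include any medications that started and stopped prior to the first administration of UCB7665". The second is the class rule: "The ATC Therapeutic Subgroup code (Level 2) 'IMMUNE SERA AND IMMUNOGLOBULINS' will be utilized". Nothing else in section 4.8 narrows it.

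The neighbouring rules are built differently. The corticosteroid subgroup refers to a list of codes in section 13.1. The two subgroups on past ITP therapy use this definition: "The past ITP therapy is defined as procedure history related to ITP or past medication related to ITP", with relation to ITP taken from the CRF.

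Section 6.4 summarises medications by "WHODD Anatomical Main Group [Level 1], Therapeutic Subgroup [Level 2] and PT". The medication listing also carries "frequency, formulation, route of administration, indication, category".

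The subgroup is used for the platelet summaries (8.1.2), the responder rates (8.1.3.3) and total IgG (9.2.2). Section 8.2.1.1 adds: "Summary tabulations for Clinical Response by dose arm will be repeated according to past intravenous immunoglobulin medication (Yes/No)".

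**The concern.** The label names a product given by one route. The rule selects a whole therapeutic class by name. If the class holds anything other than intravenous normal immunoglobulin, subjects never given IVIg can enter the 'Yes' stratum.

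These tables will be read as IVIg-experienced against IVIg-naive subjects. The comparison invites a literal reading here, because change in total IgG is a secondary objective and change in platelet count is the efficacy objective. The strata are also small: section 2.3 plans 15 subjects in each of Dose Arms 1 and 2 and 6 to 12 in each of Dose Arms 3 to 5, and each arm is split again by the subgroup.

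**Working it through.** The SAP states no figure on this point, so there is none to reproduce. The check is mainly of text, followed by an illustration with assumed counts.

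**Text, side by side**

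| Element | Label (4.8) | Rule (4.8 with 6.4.1) |
|---|---|---|
| Product | Immunoglobulin | Immune sera or immunoglobulins |
| Route | Intravenous | Not stated |
| Timing | Past | Started and stopped before first dose |
| Coding level | Not stated | Level 2 class |

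The rule is wider than the label on product and on route. This follows from the class name alone and needs no list of the class contents.

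A narrower rule was available. Preferred term lies below Level 2 in the coding used in section 6.4, and route is a listed field. Section 8.1.4 already names commercially available IVIg as a product when it defines rescue medication.

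**Share of the 'Yes' stratum that one or two wrong assignments make up**

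Let y be the number of true IVIg subjects and m the number wrongly added. Both are assumed. The share is m / (y + m).

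| y | m = 1 | m = 2 |
|---|---|---|
| 2 | 1/3 = 33% | 2/4 = 50% |
| 4 | 1/5 = 20% | 2/6 = 33% |
| 6 | 1/7 = 14% | 2/8 = 25% |
| 8 | 1/9 = 11% | 2/10 = 20% |

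**Effect on a responder table**

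Assume an arm of 12, truly split 6 and 6, with 3/6 responders in each stratum, so the true difference is zero. Move one subject who never had IVIg from 'No' to 'Yes':

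- If that subject is a responder: 4/7 = 57.1% against 2/5 = 40.0%, a difference of +17.1 points.
- If that subject is a non-responder: 3/7 = 42.9% against 3/5 = 60.0%, a difference of −17.1 points.

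Section 8.1.3.3 specifies 90% Wilson intervals. With z = 1.645, so z² = 2.706, the interval is [p + z²/(2n) ± z·√(p(1−p)/n + z²/(4n²))] / (1 + z²/n).

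- 4/7: (0.5714 + 0.1933 ± 1.645 × 0.2209) / 1.3866, or about 29% to 81%.
- 2/5: (0.4000 + 0.2706 ± 1.645 × 0.2740) / 1.5412, or about 14% to 73%.

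The intervals overlap over most of their length. One wrong assignment can move the point estimates by 17 points in either direction, but the printed intervals would not support a claimed difference.

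**The case against.** - **No affected subject is shown.** A reader might infer that subjects without IVIg have in fact been placed in the 'Yes' group. The SAP does not support that. It shows what the rule would do to such a subject, not that one was enrolled or had such a product recorded. This objection stands and limits the point to the rule.
- **The rule was written with data in view.** The class-based rule entered with SAP Amendment 3 (24 Jan 2019), after the December 2018 data evaluation meeting. It may have been chosen because the class captured the intended entries. That is plausible, but the SAP does not say so. If every entry is IVIg, a narrower rule changes no table.
- **The missing ITP condition is not a fault.** A reader might infer from the neighbouring rules that relation to ITP should also be required. Those rules concern past ITP therapy, whereas this one concerns past IVIg exposure. Such a condition would put a subject given IVIg for another indication into 'No', which is the same error in the other direction. This objection stands.
- **The effect is small and has no fixed direction.** The outputs are descriptive, no subgroup hypothesis test is planned, and the intervals above overlap widely. This stands too, and a reader should not infer a bias towards either stratum.
- **Errors would be visible.** The section 6.4 listing shows reported term, route and indication. That permits checking, but the subgroup tables would still be printed as assigned.

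**Conclusion.** The point holds as a mismatch between a label and its rule. Section 4.8 calls the subgroup past IVIg but assigns it from a class that is wider by its own name, and no other section narrows it. A subject whose only past entry in the class is an immune serum or a non-intravenous immunoglobulin would be counted as IVIg-experienced in four sets of subgroup tables.

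The size is modest. The number of affected subjects is unknown and may be zero. The primary safety variable and the planned tests do not depend on this subgroup. The case for correcting it is that, in strata of this size, a single wrong entry is a visible share of the 'Yes' group (11% to 33% for eight down to two true IVIg subjects), and the data needed to prevent it are already held.

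The conclusion on the rule rests on the wording of the class name and of section 6.4.1. The percentages rest on assumed counts and serve only to show scale.

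**What to change.** Replace the class sentence for this subgroup in section 4.8 with a rule to this effect: past IVIg is 'Yes' if a past medication within this class has a preferred term for normal human immunoglobulin and a recorded intravenous route. Records with missing or unclear route are settled by medical review of the qualifying terms before database lock. Without that last step, a true IVIg record with no route would fall to 'No'.

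Do not add a condition on relation to ITP.

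If the sponsor prefers to keep the broad class, relabel the subgroup as past immune sera/immunoglobulins in section 4.8 and in every table that uses it. The tables would then be true to their label but would no longer address IVIg experience.

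The cost is a sentence or two in section 4.8, a filter on fields already in the medication data, and one short review of terms. No new data are needed. Section 1 requires a further SAP amendment for a change of definition before database lock, so the change would go in one.
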